6.6. Concomitant medications/products and concomitant vaccinations

At each study visit/contact, the investigator should question the subject about any medication/product taken and vaccination received by the subject.

6.6.1. Recording of concomitant medications/products and concomitant vaccinations

The following concomitant medications/products/vaccines must be recorded in the eCRF if administered during the indicated recording period:

- All concomitant medications/products, except vitamins and dietary supplements, administered 30 days following each dose of study vaccine.
- Any concomitant vaccination administered in the period starting 30 days before the first dose of study vaccine and ending at the last study visit.
- Prophylactic medication (i.e. medication administered in the absence of ANY symptom and in anticipation of a reaction to the vaccination).

E.g. an anti-pyretic is considered to be prophylactic when it is given in the absence of fever and any other symptom, to prevent fever from occurring (fever is defined as an oral or axillary temperature $\geq 37.5^{\circ}\text{C}$ for oral or axillary route).

- Any concomitant medications/products/vaccines listed in Section 6.6.2 during the entire study period.
- Any concomitant medication/product/vaccine relevant to a SAE* or administered at any time during the study period for the treatment of a SAE*.

* SAEs that are required to be reported per protocol.

6.6.2. Concomitant medications/products/vaccines that may lead to the elimination of a subject from ATP analyses

The use of the following concomitant medications/products/vaccines will not require withdrawal of the subject from the study but may determine a subject's evaluability in the ATP analysis. See Section 10.4 for study cohorts/ data sets to be analysed.

- Any investigational or non-registered product (drug or vaccine) other than the study vaccines used during the study period.
- Immunosuppressants or other immune-modifying drugs administered chronically (i.e. more than 14 days) during the study period. For corticosteroids, this will mean prednisone ≥ 20 mg/day, or equivalent. Topical steroids are allowed.
- Long-acting immune-modifying drugs administered at any time during the study period (e.g. infliximab).
- A vaccine not foreseen by the study protocol administered during the period starting from 30 days before the first dose and ending 30 days after the last dose of vaccine with the exception of any influenza vaccine or pneumococcal vaccine (Step 2 only)

which may be administered \geq 15 days preceding or following any study vaccine dose.*

* In case an emergency mass vaccination for an unforeseen public health threat (e.g. a pandemic) is organised by the public health authorities, outside the routine immunisation programme, the time period described above can be reduced if necessary for that vaccine provided it is licensed and used according to its summary of product characteristics or prescribing information and according to the local governmental recommendations and provided a written approval of the Sponsor is obtained.

- Immunoglobulins and/or any blood products administered during the study period.

6.7. Intercurrent medical conditions that may lead to elimination of a subject from ATP analyses

At each study visit subsequent to the first vaccination visit, it must be verified if the subject has experienced or is experiencing any intercurrent medical condition(s) requiring medical attention. If it is the case, the condition(s) must be recorded in the eCRF.

Subjects may be eliminated from the ATP cohort for immunogenicity if, during the study, they incur a condition that has the capability of altering their immune response (e.g. confirmed immunosuppressive or immunodeficient condition, including HIV).

7. HEALTH ECONOMICS

Not applicable.

8. SAFETY

The investigator or site staff is/are responsible for the detection, documentation and reporting of events meeting the criteria and definition of an AE or SAE as provided in this protocol.

Each subject will be instructed to contact the investigator immediately should he/she manifest any signs or symptoms they perceive as serious.

8.1. Safety definitions

8.1.1. Definition of an adverse event

An AE is any untoward medical occurrence in a clinical investigation subject, temporally associated with the use of a medicinal product, whether or not considered related to the medicinal product.

An AE can therefore be any unfavourable and unintended sign (including an abnormal laboratory finding), symptom, or disease (new or exacerbated) temporally associated with the use of a medicinal product. For marketed medicinal products, this also includes failure to produce expected benefits (i.e. lack of efficacy), abuse or misuse.

Examples of an AE include:

- Worsening of a chronic or intermittent pre-existing condition including either an increase in frequency and/or intensity of the condition.
- New conditions detected or diagnosed after investigational vaccines administration even though they may have been present prior to the start of the study.
- Signs, symptoms, or the clinical sequelae of a suspected interaction.
- Signs, symptoms, or the clinical sequelae of a suspected overdose of either investigational vaccine or a concurrent medication (overdose per se should not be reported as an AE/SAE).
- Signs, symptoms temporally associated with vaccine administration.
- Pre- or post-treatment events that occur as a result of protocol-mandated procedures (i.e. invasive procedures, modification of subject's previous therapeutic regimen).

AEs to be recorded as endpoints (solicited AEs) are described in Section 8.1.3. All other AEs will be recorded as UNSOLICITED AEs.

Examples of an AE DO NOT include:

- Medical or surgical procedures (*e.g.* endoscopy, appendectomy); the condition that leads to the procedure is an AE/SAE.
- Situations where an untoward medical occurrence did not occur (*e.g.* social and/or convenience admission to a hospital, admission for routine examination).
- Anticipated day-to-day fluctuations of pre-existing disease(s) or condition(s) present or detected at the start of the study that do not worsen.
- Pre-existing conditions or signs and/or symptoms present in a subject prior to the first study vaccination. These events will be recorded in the medical history section of the eCRF.

8.1.2. Definition of a serious adverse event

A SAE is any untoward medical occurrence that:

- a. Results in death,
- b. Is life-threatening,

Note: The term 'life-threatening' in the definition of 'serious' refers to an event in which the subject was at risk of death at the time of the event. It does not refer to an event, which hypothetically might have caused death, had it been more severe.

- c. Requires hospitalisation or prolongation of existing hospitalisation,

Note: In general, hospitalisation signifies that the subject has been admitted at the hospital or emergency ward for observation and/or treatment that would not have been appropriate in the physician's office or in an out-patient setting. Complications that occur during hospitalisation are also considered AEs. If a complication prolongs hospitalisation or fulfils any other serious criteria, the event will also be considered serious. When in doubt as to whether 'hospitalisation' occurred or was necessary, the AE should be considered serious.

Hospitalisation for elective treatment of a pre-existing condition (known or diagnosed prior to informed consent signature) that did not worsen from baseline is NOT considered an AE.

- d. Results in disability/incapacity, OR

Note: The term disability means a substantial disruption of a person's ability to conduct normal life functions. This definition is not intended to include experiences of relatively minor medical significance such as uncomplicated headache, nausea, vomiting, diarrhoea, influenza like illness, and accidental trauma (e.g. sprained ankle) which may interfere or prevent everyday life functions but do not constitute a substantial disruption.

- e. Is a congenital anomaly/birth defect in the offspring of a study subject.

Medical or scientific judgement should be exercised in deciding whether reporting is appropriate in other situations, such as important medical events that may not be immediately life-threatening or result in death or hospitalisation but may jeopardise the subject or may require medical or surgical intervention to prevent one of the other outcomes listed in the above definition. These should also be considered serious.

Examples of such events are invasive or malignant cancers, intensive treatment in an emergency room or at home for allergic bronchospasm, blood dyscrasias or convulsions that do not result in hospitalisation.

8.1.3. **Solicited adverse events**

Solicited local and general AEs occurring during a 7-day follow-up period after each vaccination (i.e. the day of vaccination and the 6 subsequent days), as well as unsolicited AEs occurring during a 30-day follow-up period after each vaccination (i.e. the day of vaccination and the 29 subsequent days), will be reported via paper Diary Cards for vaccine reactogenicity and recorded via the appropriate section of the eCRF.

8.1.3.1. **Solicited local (injection-site) adverse events**

The following local (injection-site) AEs will be solicited:

Table 16 Solicited local adverse events

| |
|----------------------------|
| Pain at injection site |
| Redness at injection site |
| Swelling at injection site |

8.1.3.2. Solicited general adverse events

The following general AEs will be solicited:

Table 17 Solicited general adverse events

| |
|--|
| Fever |
| Headache |
| Fatigue |
| Myalgia |
| Gastrointestinal symptoms ^a |

^a Gastrointestinal symptoms include nausea, vomiting, diarrhoea and/or abdominal pain.

Note: Temperature will be recorded in the evening. Should additional temperature measurements be performed at other times of day, the highest temperature will be recorded in the eCRF.

8.1.4. Clinical laboratory parameters and other abnormal assessments qualifying as adverse events or serious adverse events

In absence of diagnosis, abnormal laboratory findings (e.g. clinical chemistry, haematology, urinalysis) or other abnormal assessments that are judged by the investigator to be clinically significant will be recorded as AE or SAE if they meet the definition of an AE or SAE (refer to Sections 8.1.1 and 8.1.2). Clinically significant abnormal laboratory findings or other abnormal assessments that are present at baseline and significantly worsen following the start of the study will also be reported as AEs or SAEs.

The investigator will exercise his or her medical and scientific judgement in deciding whether an abnormal laboratory finding or other abnormal assessment is clinically significant.

8.1.5. Adverse events of specific interest (potential immune-mediated diseases)

Potential immune-mediated diseases (pIMDs) are a subset of AEs that include autoimmune diseases and other inflammatory and/or neurologic disorders of interest which may or may not have an autoimmune aetiology. AEs that need to be recorded and reported as pIMDs include those listed in [Table 18](#).

However, the investigator will exercise his/her medical and scientific judgement in deciding whether other diseases have an autoimmune origin (i.e. pathophysiology involving systemic or organ-specific pathogenic autoantibodies) and should also be recorded as a pIMD.

Table 18 List of potential immune-mediated diseases

| Neuroinflammatory disorders | Musculoskeletal disorders | Skin disorders |
|---|--|--|
| 
 • Cranial nerve disorders, including paralyses/paresis (e.g. Bell's palsy) • Optic neuritis • Multiple sclerosis • Transverse myelitis • Guillain-Barré syndrome, including Miller Fisher syndrome and other variants • Acute disseminated encephalomyelitis, including site specific variants: e.g. non-infectious encephalitis, encephalomyelitis, myelitis, myeloradiculoneuritis • Myasthenia gravis, including Lambert-Eaton myasthenic syndrome • Immune-mediated peripheral neuropathies and plexopathies, (including chronic inflammatory demyelinating polyneuropathy, multifocal motor neuropathy and polyneuropathies associated with monoclonal gammopathy). • Narcolepsy | 
 • Systemic lupus erythematosus and associated conditions • Systemic sclerosis (Systemic sclerosis), including diffuse systemic form and CREST syndrome • Idiopathic inflammatory myopathies, including dermatomyositis • Polymyositis • Antisynthetase syndrome • Rheumatoid arthritis, and associated conditions including juvenile chronic arthritis and Still's disease • Polymyalgia rheumatica • Spondyloarthritis, including ankylosing spondylitis, reactive arthritis (Reiter's Syndrome) and undifferentiated spondyloarthritis • Psoriatic arthropathy • Relapsing polychondritis • Mixed connective tissue disorder | 
 • Psoriasis • Vitiligo • Erythema nodosum • Autoimmune bullous skin diseases (including pemphigus, pemphigoid and dermatitis herpetiformis) • Alopecia areata • Lichen planus • Sweet's syndrome • Localised Scleroderma (Morphea) |
| Vasculitides | Blood disorders | Others |
| 
 • Large vessels vasculitis including: giant cell arteritis such as Takayasu's arteritis and temporal arteritis. • Medium sized and/or small vessels vasculitis including: polyarteritis nodosa, Kawasaki's disease, microscopic polyangiitis, Wegener's granulomatosis, Churg-Strauss syndrome (allergic granulomatous angiitis), Buerger's disease (thromboangiitis obliterans), necrotizing vasculitis and anti-neutrophil cytoplasmic antibody (ANCA) positive vasculitis (type unspecified), Henoch-Schonlein purpura, Behcet's syndrome, leukocytoclastic vasculitis. | 
 • Autoimmune hemolytic anemia • Autoimmune thrombocytopenia • Antiphospholipid syndrome • Pernicious anemia • Autoimmune aplastic anaemia • Autoimmune neutropenia • Autoimmune pancytopenia | 
 • Autoimmune glomerulonephritis (including IgA nephropathy, glomerulonephritis rapidly progressive, membranous glomerulonephritis, membranoproliferative glomerulonephritis, and mesangioproliferative glomerulonephritis) • Ocular autoimmune diseases (including autoimmune uveitis and autoimmune retinopathy) • Autoimmune myocarditis/cardiomyopathy • Stevens-Johnson syndrome • Sjögren's syndrome • Idiopathic pulmonary fibrosis • Goodpasture syndrome • Raynaud's phenomenon |

| Liver disorders | Gastrointestinal disorders | Endocrine disorders |
|---|---|---|
| 
 Autoimmune hepatitis Primary biliary cirrhosis Primary sclerosing cholangitis Autoimmune cholangitis | 
 Inflammatory Bowel disease, including Crohn's disease, ulcerative colitis, microscopic colitis, ulcerative proctitis Celiac disease Autoimmune pancreatitis | 
 Autoimmune thyroiditis (including Hashimoto thyroiditis) Grave's or Basedow's disease Diabetes mellitus type I Addison's disease Polyglandular autoimmune syndrome Autoimmune hypophysitis |

When there is enough evidence to make any of the above diagnoses, the AE must be reported as a pIMD. Symptoms, signs or conditions which might (or might not) represent the above diagnoses, should be recorded and reported as AEs but not as pIMDs until the final or definitive diagnosis has been determined, and alternative diagnoses have been eliminated or shown to be less likely.

In order to facilitate the documentation of pIMDs in the eCRF, a pIMD standard questionnaire and a list of preferred terms (PTs) and PT codes corresponding to the above diagnoses will be available to investigators at study start.

8.2. Events or outcomes not qualifying as adverse events or serious adverse events

Pregnancy

Female subjects who are pregnant or lactating at the time of vaccination must not receive additional doses of study vaccines but may continue other study procedures at the discretion of the investigator.

While pregnancy itself is not considered an AE or SAE, any adverse pregnancy outcome or complication or elective termination of a pregnancy for medical reasons will be recorded and reported as an AE or a SAE.

Note: The pregnancy itself should always be recorded on an electronic pregnancy report.

The following should always be considered as SAE and will be reported as described in Sections 8.4.1 and 8.4.3:

- Spontaneous pregnancy loss, including:
 - spontaneous abortion, (spontaneous pregnancy loss before/at 22 weeks of gestation)
 - ectopic and molar pregnancy
 - stillbirth (intrauterine death of foetus after 22 weeks of gestation).

Note: the 22 weeks cut-off in gestational age is based on WHO-ICD 10 noted in the EMA Guideline on pregnancy exposure [[EMA](#), 2006]. It is recognized that national regulations might be different.

- Any early neonatal death (i.e. death of a live born infant occurring within the first 7 days of life).

- Any congenital anomaly or birth defect (as per [CDC MACDP] guidelines) identified in the offspring of a study subject (either during pregnancy, at birth or later) regardless of whether the foetus is delivered dead or alive. This includes anomalies identified by prenatal ultrasound, amniocentesis or examination of the products of conception after elective or spontaneous abortion.

Furthermore, any SAE occurring as a result of a post-study pregnancy AND considered by the investigator to be reasonably related to the investigational vaccines will be reported to GSK Biologicals as described in Section 8.4.3. While the investigator is not obligated to actively seek this information from former study participants, he/she may learn of a pregnancy through spontaneous reporting.

8.3. Detecting and recording adverse events, serious adverse events and pregnancies

8.3.1. Time period for detecting and recording adverse events, serious adverse events and pregnancies

All AEs starting within 30 days following administration of each dose/ of study vaccines (Day 0 to Day 30) must be recorded into the appropriate section of the eCRF, irrespective of intensity or whether or not they are considered vaccination-related.

The time period for collecting and recording SAEs will begin at the first receipt of study vaccines and will end at study conclusion. See Section 8.4 for instructions on reporting of SAEs.

All AEs/SAEs leading to withdrawal from the study will be collected and recorded from the time of the first receipt of study vaccines until study conclusion.

In addition to the above-mentioned reporting requirements and in order to fulfil international reporting obligations, SAEs that are related to study participation (i.e. protocol-mandated procedures, invasive tests, a change from existing therapy) or are related to a concurrent GSK medication/vaccine will be collected and recorded from the time the subject consents to participate in the study until she/he is discharged from the study.

The time period for collecting and recording of pIMDs will begin at the first receipt of study vaccine and will end at study conclusion. See Section 8.4 for instructions on reporting of pIMDs.

The time period for collecting and recording pregnancies will begin at the first receipt of study vaccine and will end at study conclusion. See Section 8.4 for instructions on reporting of pregnancies.

The time period for collecting and recording of intercurrent medical conditions requiring medical attention will begin at the first receipt of study vaccine and will end at study conclusion.

Table 19 Reporting periods for collecting safety information

| Event | Screening Visit* | Visit 1 | 7 d post | 30 d post | Visit 4 | 7 d post | 30 d post | Study Conclusion |
|--|------------------|---------|----------|-----------|---------|----------|-----------|------------------|
| | | Dose 1 | Dose 1 | Dose 1 | Dose 2 | Dose 2 | Dose 2 | |
| | | Day 0 | Day 6 | Day 29 | Day 60 | Day 66 | Day 89 | Day 210 |
| Solicited local and general AEs | | | | | | | | |
| Unsolicited AEs | | | | | | | | |
| AEs/SAEs leading to withdrawal from the study | | | | | | | | |
| SAEs | | | | | | | | |
| SAEs related to study participation or concurrent GSK medication/vaccine | | | | | | | | |
| Pregnancies | | | | | | | | |
| plMDs | | | | | | | | |
| Intercurrent medical conditions requiring medical attention | | | | | | | | |

d = day follow-up period.

* i.e. consent obtained.

The double-bordered lines indicate timings of vaccination.

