8.3.2. Post-study adverse events and serious adverse events

A post-study AE/SAE is defined as any event that occurs outside of the AE/SAE reporting period defined in [Table 19](#). Investigators are not obligated to actively seek AEs or SAEs in former study participants. However, if the investigator learns of any SAE at any time after a subject has been discharged from the study, and he/she considers the event reasonably related to the investigational vaccines, the investigator will promptly notify the Study Contact for Reporting SAEs.

8.3.3. Evaluation of adverse events and serious adverse events**8.3.3.1. Active questioning to detect adverse events and serious adverse events**

As a consistent method of collecting AEs, the subject should be asked a non-leading question such as:

‘Have you felt different in any way since receiving the vaccine or since the previous visit?’

When an AE/SAE occurs, it is the responsibility of the investigator to review all documentation (e.g. hospital progress notes, laboratory and diagnostics reports) relative to the event. The investigator will then record all relevant information regarding an AE/SAE in the eCRF. The investigator is not allowed to send photocopies of the subject's medical records to GSK Biologicals instead of appropriately completing the eCRF. However, there may be instances when copies of medical records for certain cases are requested by GSK Biologicals. In this instance, all subject identifiers will be blinded on the copies of the medical records prior to submission to GSK Biologicals.

The investigator will attempt to establish a diagnosis pertaining to the event based on signs, symptoms, and/or other clinical information. In such cases, the diagnosis should be documented as the AE/SAE and not the individual signs/symptoms.

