10. STATISTICAL METHODS

10.1. Primary endpoints

- Occurrence of each solicited local and general AE, during a 7-day follow-up period (i.e. day of vaccination and 6 subsequent days) post-Dose 1 and post-Dose 2, in all subjects, in all vaccine groups.
- Occurrence of any unsolicited AEs, during a 30-day follow-up period (i.e. day of vaccination and 29 subsequent days) post-Dose 1 and post-Dose 2, in all subjects, in all vaccine groups.

- Occurrence of haematological and biochemical laboratory abnormalities, after vaccination, in all subjects, in all vaccine groups:
 - Any haematological (RBC, WBC and differential count, platelets count and haemoglobin level) or biochemical (ALT, AST and creatinine) laboratory abnormality on Day 7, Day 60, Day 67, Day 210 and Day 420.
- Occurrence of any SAE, occurring from first vaccination (Day 0) to study conclusion (Day 420) in all subjects, in all vaccine groups.
- Occurrence of any pIMD occurring from first vaccination (Day 0) to study conclusion (Day 420) in all subjects, in all vaccine groups.

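### Table 19 dates study conclusion at Day 210 while the SAE and pIMD primary endpoints run to Day 420, so the protocol gives conflicting reporting instructions for Days 211 to 420

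*Protocol*

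**What the plan says.** Table 19 in Protocol 8.3.1 sets out the reporting periods for safety information. Its column headings end "7 d post | 30 d post | Visit 4 | 7 d post | 30 d post | Study Conclusion", and the days beneath them end "Day 60 | Day 66 | Day 89 | Day 210". The Study Conclusion column is therefore dated Day 210, and the table has no Visit 7 or Day 420 column.

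The running text of 8.3.1 gives no day. For SAEs: "The time period for collecting and recording SAEs will begin at the first receipt of study vaccines and will end at study conclusion". For pIMDs: "The time period for collecting and recording of pIMDs will begin at the first receipt of study vaccine and will end at study conclusion". Pregnancies, intercurrent conditions and AEs or SAEs leading to withdrawal are also collected up to study conclusion.

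Two later sections depend on this period:

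- Section 8.3.2: "A post-study AE/SAE is defined as any event that occurs outside of the AE/SAE reporting period defined in" Table 19.
- Section 8.4.1 requires prompt reporting of SAEs and pIMDs that fall within the Section 8.3 period, on the 24-hour timeframes of Table 21.

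Section 10.1 does give the day. For SAEs: "Occurrence of any SAE, occurring from first vaccination (Day 0) to study conclusion (Day 420) in all subjects, in all vaccine groups". For pIMDs: "Occurrence of any pIMD occurring from first vaccination (Day 0) to study conclusion (Day 420) in all subjects, in all vaccine groups". Section 5.1 of the current SAP repeats both windows.

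**The concern.** Two of the five primary endpoints, SAEs and pIMDs, are counted to Day 420. The table that tells sites when reporting ends closes at Day 210. An isolated slip in descriptive text would hardly matter, but this figure is used: 8.3.2 takes its definition from the table, and the 8.4.1 reporting window points to the section that contains it. Nothing else in Section 8.3 dates study conclusion, so a reader of that section alone would take Day 210.

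Sites reading different sections could handle the same event differently. An SAE on Day 300 is an endpoint event under 10.1 and a post-study event under the literal wording of 8.3.2. An event treated as outside the prompt-reporting window might surface only at Visit 8, or be recorded incompletely.

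For pIMDs the setting adds weight. A theoretical risk of vaccine-induced autoimmune disease is the one risk listed in 1.3.1, and close pIMD monitoring is its mitigation. Section 8.1.5 also holds back the pIMD label until a definitive diagnosis is made, so some cases may be classified well after first symptoms.

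**Working it through.** **1. Can Day 210 be reproduced as the end of study?** Section 3.1 says each subject takes part for about 15 months from screening. Screening may be 1 to 28 days before Day 0 (Table 7). Months = (end day + screening interval) / 30.4375.

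- End at Day 420: (420 + 1)/30.4375 = 13.8; (420 + 28)/30.4375 = 14.7. At the outer edge of the Visit 8 window, (440 + 28)/30.4375 = 15.4. This agrees with about 15 months.
- End at Day 210: (210 + 1)/30.4375 = 6.9; (210 + 28)/30.4375 = 7.8. This does not.

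**2. The dated statements side by side.**

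| Place | End of period |
|---|---|
| Protocol 8.3.1, Table 19 | Day 210 |
| Protocol 10.1, SAE and pIMD endpoints | Day 420 |
| Protocol 3.1, Epoch 002 | Visit 8, Day 420 |
| Protocol Table 7 | Visit 8 at 420 days (420 to 440 allowed) |
| Protocol Tables 5 and 6, SAE and pIMD recording, study conclusion | Day 420 |
| Protocol 10.8.1, final SAE and pIMD analysis | Day 420 |
| SAP 5.1, SAE and pIMD endpoints | Day 420 |

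Table 19 stands alone. The changes shown in Appendix D do not touch it, so Day 210 is current text.

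**3. Span in conflict.** Days 211 to 420 are 420 − 210 = 210 days.

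- Share of the endpoint window: 210/420 = 50%.
- Share of the time after Dose 2 on Day 60: 210/(420 − 60) = 210/360 = 58%.
- In person-time, for 120 subjects with no dropout: 120 × 210/365.25 = 69 of 120 × 420/365.25 = 138 person-years.

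**4. Possible delay.** If an event just after Visit 7 were first recorded at Visit 8, the gap could reach 420 − 210 = 210 days, or 440 − 210 = 230 days at the edge of the Visit 8 window.

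**5. What the conflict reaches.** The 8.3.2 definition names AEs and SAEs, not pIMDs; 8.4.1 covers both SAEs and pIMDs. The Table 19 rows for pregnancies, withdrawal AEs and intercurrent conditions share the same last column.

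**The case against.** The strongest reply is that no careful site would stop at Day 210. Section 3.1 makes adherence to the Section 5.5 procedures mandatory, and Tables 5 and 6 there call for eCRF recording of SAEs and pIMDs at Day 420. Section 8.5.1.1 keeps unresolved SAEs and pIMDs under review to the end of the study. Sections 8.4.3 and 8.4.4 repeat the 24-hour rule for any study subject without naming a period. All of this stands. It is why the consequence is a risk and not an established loss.

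A reader might go further and infer from 8.3.2 that sites are released from seeking events after Day 210. The text does not support that. The relaxation reads "Investigators are not obligated to actively seek AEs or SAEs in former study participants", and the duty to notify only related SAEs applies once a subject has been discharged. Under 9.1 a subject completes the study by returning for the concluding visit, so someone awaiting Visit 8 is neither former nor discharged. Only the definitional sentence of 8.3.2 conflicts with 10.1.

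The table might also have been damaged in conversion from PDF, which happens elsewhere in this protocol, and the bars marking each row's period are not visible. Equal cell counts in the heading and day rows (nine each) do not settle this, since losing a whole column would keep them equal. However, Study Conclusion and Day 210 are both present, in the same position, with no Visit 7 heading or Day 420 cell left over. Conversion error is possible but unlikely; a look at the issued table would settle it.

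**Conclusion.** The contradiction is real and should be corrected. Table 19 gives Day 210 where the rest of the protocol's schedule and the SAP endpoints give Day 420, and two reporting rules rest on the Section 8.3 period. The instructions conflict for 210 of 420 days. What is at risk is inconsistent classification of AEs and SAEs, and late or incomplete reporting of SAEs and pIMDs, in that stretch.

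Two stronger readings do not hold. The 69 person-years are the span over which the instructions disagree, not data lost, because Visit 8 recording is still scheduled for everyone. Nor do the documents say that the long follow-up exists to catch late-onset disease; Epoch 002 also serves antibody persistence.

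The design itself consistently runs to Day 420, so this is an internal contradiction and not a flaw in the choice of follow-up. The conclusion assumes that the issued Table 19 reads as described. The person-year figures also assume 120 subjects and no dropout.

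**What to change.** Check the issued Table 19, then date its Study Conclusion column Day 420. Run the SAE, pIMD, pregnancy, withdrawal-AE and intercurrent-condition periods to that day. If Visit 7 is worth showing, add a separate Day 210 column. Sections 8.3.1, 8.3.2 and 8.4.1 then agree with 10.1 without rewording.

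Notify sites, and state in the notice that a subject who has not yet had Visit 8 is still within the reporting period.

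While aligning end days, also reconcile the analysis table in SAP 9.1, which labels the final analysis as running to Day 450, with the SAP's own Visit 8 at Day 420.

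The cost is one table in a protocol amendment and a site notification. No visit, sample or procedure is added, because Visit 8 and its SAE and pIMD recording are already scheduled.
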